### Guidelines for Preparing a Research Protocol

#### Instructions:

- You do not need to complete this document if you are submitting an *Application for Exemption* or *Application for a Chart Review*.
- Do not use this template if:
  - Your study involves an FDA regulated product. In this case, use the *Clinical Trial Protocol Template*.
  - Your study has a protocol from a sponsor or cooperative group. In this case, use the *Protocol Plus*.
  - Your study is a registry or repository for data and/or samples, In this case, use *Protocol Template – Registry Studies*.
- If a section of this protocol is not applicable, please indicate such.
- Do not delete any of the text contained within this document.
- Please make sure to keep an electronic copy of this document. You will need to use it, if you make modifications in the future.
- Start by entering study information into the table above, according to these rules:
  - Protocol Title: Include the full protocol title as listed on the application.
  - Investigator: include the principal investigator's name as listed on the application form
  - Date Revised: Indicate the date at which the protocol was last revised
  - IRB Number: Indicate the assigned IRB number, when known. At initial submission, this row will be left blank.
- Once the table information is entered, proceed to page 2 and complete the rest of the form.

↓ Continue to next page to begin entering information about this study ↓

## 1. PREVIOUS STUDY HISTORY

Has this study ever been reviewed and rejected/disapproved by another IRB prior to submission to this IRB?

No  Yes – if yes, please explain: ]

## 2. BRIEF SUMMARY OF RESEARCH

- *The summary should be written in language intelligible to a moderately educated, non-scientific layperson.*
- *It should contain a clear statement of the rationale and hypothesis of your study, a concise description of the methodology, with an emphasis on what will happen to the subjects, and a discussion of the results.*
- *This section should be ½ page*

This pilot study will utilize a Personalized Trials model to evaluate an individual participant's experience with a Mind-Body Intervention (MBI) strategy for self-reported perceived stress and short sleep duration of at least 3 months duration. Components of the MBI include mindfulness, yoga and guided walking, each assigned in 2-week block sequences for a total period of 12 weeks. MBI components will be delivered via 30-minute videos and will be accessed three times per week. Participants will be sent a Fitbit device to track their sleep and activity. Participants will be asked several questions a day sent via text message about their sleep quality, as well as bi-weekly questions about their health including stress, fatigue, concentration, confidence, mood, and pain levels to demonstrate relevant secondary impacts of sleep quality. Stress, anxiety and depression will be measured using validated assessments. Following 12 weeks of intervention, participants will continue to have their sleep duration monitored for a two-week follow-up period. After the end of the 16-week trial, participants will receive a summary of their observed data in a personalized report.

Results from this pilot study will inform the future development of N-of-1 methodology in the research and clinical space aimed at addressing the health and wellness needs of adults biologically assigned female at birth who are 40-60 years of age.]

## 3. INTRODUCTION/BACKGROUND MATERIAL/PRELIMINARY STUDIES AND SIGNIFICANCE

- *Describe and provide the results of previous work by yourself or others, including animal studies, laboratory studies, pilot studies, pre-clinical and/or clinical studies involving the compound or device to be studied.*
- *Include information as to why you are conducting the study and how the study differs from what has been previously researched, including what the knowledge gaps are.*
- *Describe the importance of the knowledge expected to result*

This project represents a pilot project under the funding umbrella of the NIA-funded grant establishing the Roybal Center for Personalized Trials at Northwell Health. The Center's mission is to test use cases appropriate for N-of-1 methodology and develop promising, innovative behavioral interventions along the NIH Stage model pathway, with a focus on addressing the health and wellness needs of an aging population.

Right now, clinicians are engaging in clinical encounters in which they are trying to determine the best therapy for individual patients. These encounters are likely to be unsuccessful. Clinicians rely on the best available evidence (e.g., results from parallel group, phase III randomized clinical trials; RCTs) for recommending therapies to a patient. Yet, conventional, between-group RCTs only provide estimates of the effect of therapies on the hypothetical 'average' patient in those trials. Individual patients, however, often respond differently than the hypothetical average patient in the phase III RCTs, and thus, heterogeneity of therapy response plagues clinical decisions made for an individual patient every day.

The most scientifically rigorous — and potentially transformative — method for determining optimal therapy for a patient is a single-patient (N-of-1) trial. N-of-1 trials are multiple crossover trials, usually randomized, and often masked, conducted within a single patient, with data collected objectively, continuously, and in the real-world, for a sufficient time period to determine whether the therapy is optimal for a particular patient. In many ways, Personalized or N-of-1 Trials are the foundational design for a truly patient-centered approach by serving as a clinical decision tool for patients. Historically, in introducing evidence-based medicine, Guyatt and others have described Personalized Trials as the pinnacle of the evidence-based design pyramid. Clinicians can use these techniques to monitor and make treatment decisions in chronically ill patients, of whom 25% experience adverse treatment effects. Personalized Trials are specifically designed to help patients and their clinicians make healthcare decisions that are informed by high-integrity, evidence-based information uniquely relevant to the outcomes and values important to them^4. In post-mortem assessments as to why Personalized Trials had yet to become commonly employed, proponents concluded that they were insufficiently appealing to patients or clinicians to justify the cost and effort needed to design and implement them. Specifically, Personalized Trial design specifications had mostly been driven by clinicians or researchers, with little input from patients.

### **Rationale for Selecting Sleep Duration as a Personalized Trial**

Sleep is an important and complex physiological process for maintaining optimal health. The National Sleep Foundation recommends  $\geq 7$ h of sleep per night on a regular basis for adults aged 18-60 years. During the first two COVID-19 pandemic waves, findings indicated a high prevalence of both poor sleep quality and moderate-severe stress in healthcare workers (HCWs) (either at the frontline or not), and especially amongst women. Studies conducted in a cohort of New York City HCWs (80% women,  $>50\%$  nurses, median age of 36 years) showed that during the pandemic, the rates of insomnia symptoms (e.g., short duration, poor quality sleep) were approximately 20% higher than rates reported in 2018, and revealed an association between poor sleep quality and a higher prevalence of psychological distress. Thus, evidence suggests that sleep may be a target intervention to decrease psychological distress among HCWs. While some mitigation interventions (e.g., reducing workload) have been proposed to address stress/burnout on HCWs very few have focused on women in healthcare and specifically targeted sleep as a symptom of stress. The primary goal of this pilot study is to determine if a personalized trial (N-of-1) employing a Mind-Body Intervention (MBI) can produce a meaningful increase in sleep duration among women 40-60 years of age and older working at Northwell Health. N-of-1 studies are single-patient crossover trials, where individual patients are given candidate treatments in a random sequence of alternating periods to determine the most effective treatment for that patient. In contrast to randomized controlled trials, which provide evidence on a population level, N-of-1 trials provide a method to determine what works best for the individual directly. Up to 65 women with a history of short sleep duration (defined as an average  $<7$ h per 24-h period for at least three months) will be enrolled (randomized) over a period of two years. Participants will complete a 2-week run-in period with no intervention, for baseline data collection, including bi-weekly surveys and Fitbit-derived sleep and activity data. Those who are deemed eligible and achieve at least 80% adherence of Fitbit wear and survey submission will be randomized to Arm 1 (N=30) or Arm 2 (N=30). Each arm will receive a personalized intervention comprised of three components: mindfulness, yoga and guided walking assigned in 2-week block sequences for a total period of 12 weeks. Following the intervention, all participants will be assessed over a 2-week follow-up period. Changes in average daily sleep duration will be calculated for each participant based on daily measurements between the run-in and each treatment period. The Fitbit devices will also record sleep quality components (sleep onset, sleep staging, and overall sleep score) and physiological factors (resting heart rate, heart rate variability (HRV) and activity). **We will also examine the direct and indirect relationships between perceived stress, anxiety and depression, and sleep quality assessed pre, during (bi-weekly), and post MBI.**

Participant report of poor sleep duration meets all of our criteria for selection as a use case as outlined in our umbrella grant: it has high public health burden; high heterogeneity of therapy response; multiple, evidenced-based treatments; and is high priority for a Personalized Trial approach as determined by previously interviewed clinicians and patients. A recent study of US workers found the prevalence of short sleep duration to be 37.6% and poor sleep quality to be 19.2%,

supporting the need for innovative treatments. This instance will adapt our N-of-1 trial platform to be able to deliver a three component Mind-Body Intervention with the goal of meaningfully increasing average daily sleep duration as compared with the baseline period.

### **Rationale for MBI Intervention Components:**

The three techniques included in the personalized intervention have been shown to be safe and effective in addressing sleep problems and reducing stress in middle aged women. Prior studies examining the effects of mediation, yoga, and physical activity for stress reduction found that all three interventions were associated with significant reductions in self-reported measures of stress and/or physiological measures of stress. Each of these promising behavioral interventions are theorized to improve sleep quantity and quality through targeting multiple cognitive and emotional processes that will be tested repeatedly in this proposed trial. However, stress and sleep reduction interventions often have high levels of heterogeneity of treatment effects (HTE). This personalized trial will allow us to evaluate the HTE and determine which treatment will be most effective for an individual participant.

As this is a digital (virtual) intervention, the maintenance of fidelity to the intervention delivery is expected to be identical to that found in research settings as the interventions will be delivered by a secure link to videos created by our wellness provider, Zeel. These videos have been previously used in other studies conducted by our Center, such as IRB # 21-0968 “Personalized Trial of Stress Management”.

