## **4. OBJECTIVE(S)/SPECIFIC AIMS AND HYPOTHESES**

- *A concise statement of the goal(s) of the current study.*
- *The rationale for and specific objectives of the study.*
- *The goals and the hypothesis to be tested should be stated.*

The goal of the Roybal Center for Personalized Trials is to focus on innovative, behavioral interventions aimed at promoting and improving the overall health and well-being of older adults through the conduct of fully powered, meaningful, personalized trial pilots. The goal of this project is to evaluate the effects of a combined Mind-Body Intervention on increasing sleep duration in middle aged women working in health care, and to determine which intervention component proved most effective for each individual participant

Thus, the aims of this pilot study are :

**Primary Aim:** Determine if a personalized trial testing a Mind-Body Intervention (MBI) can produce a meaningful increase in the average daily sleep duration among women 40 – 60 years of age working in healthcare.

**Exploratory Aim 1:** Evaluate the effect of the MBI on sleep quality and other physiological factors.

**Exploratory Aim 2:** Explore the role of anxiety and depression as a potential mediator between perceived stress and sleep quality before, during, and after the MBI.

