### **Analytical Plan**

**Primary Outcome** – Mean Within-Subject Difference in daily sleep duration during 3 treatment periods from baseline. Participant's sleep duration will be measured objectively using Fitbit devices and by self-reported questionnaires. The Fitbit devices will collect information continuously that will be stored in Fitabase, a secure, online portal. Participant sleep activity will be aggregated by day.

Analysis of Primary Outcome: The effect of the personalized MBI intervention on individual's sleep duration will be assessed in each arm separately. Individual changes in the average daily sleep durations between the run-in and each treatment period will be reported using mean (95% confidence intervals CIs). Bland-Altman plots will be constructed to visualize the agreement between the Fitbit reported and self-reported sleep duration. The effects of treatment on sleep duration will be assessed using generalized estimating equations (GEE) with an unstructured variance-covariance matrix for measures on the same day to that night's sleep. This model accounts for possible autocorrelation and linear trends between sleep duration across time. The GEE models will include time of day of treatment exposure (AM versus PM) as a covariate.

**Exploratory Aim 1 Outcomes** - Mean Within-Subject Difference in daily sleep quality and other physiological factors during 3 treatment periods from baseline. This aim will explore the effects of the personalized intervention on sleep quality components (sleep onset, sleep staging, and overall sleep score) and physiological factors (breathing/resting heart rate, heart rate variability (HRV) and physical activity). All these measurements will be recorded and aggregated daily by the Fitbit device.

Analysis of Exploratory Aim 1 Outcome: The effect of the personalized MBI intervention on individual's sleep quality and physiological factors will be assessed in each arm separately. Individual changes in the average daily sleep quality (e.g., score), heart rate and daily average number of steps between the run-in and each treatment period will be reported using means (95% CIs. GEE models will be employed to test the effect of the intervention of sleep quality and physiological factors.

**Exploratory Aim 2 Outcomes** – Mean Within-Subject Difference in perceived stress, anxiety and depression scores measured objectively during 3 treatment

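### The plan promises to evaluate heterogeneity of effect and find each participant's best component, but no planned analysis estimates heterogeneity and the individual results are only descriptive

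*Combined protocol and SAP*

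**What the plan says.** All references are to the combined protocol and SAP.

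- **Promise.** Section 3 (Rationale for MBI Intervention Components): "This personalized trial will allow us to evaluate the HTE and determine which treatment will be most effective for an individual participant". Section 4 sets a goal "to determine which intervention component proved most effective for each individual participant", next to the goal for the group effect. It is not one of the three listed aims.
- **Primary Aim.** Section 4 asks whether the intervention "can produce a meaningful increase in the average daily sleep duration among women 40 – 60 years of age working in healthcare". This is a population average.
- **Model.** Section 12 (Analytical Plan): "The effects of treatment on sleep duration will be assessed using generalized estimating equations (GEE"), arm by arm, with an unstructured covariance matrix. One covariate is named: "The GEE models will include time of day of treatment exposure (AM versus PM) as a covariate". No participant-specific treatment term is stated. Mixed models appear only for the mediation analysis of Exploratory Aim 2.
- **Individual results.** Section 12: "Individual changes in the average daily sleep durations between the run-in and each treatment period will be reported using mean (95% confidence intervals CIs"). Section 3 agrees: "Changes in average daily sleep duration will be calculated for each participant based on daily measurements between the run-in and each treatment period". Section 11 adds a personal report that summarises each participant's observed data in relation to the components.

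**The concern.** A GEE returns one average coefficient per component and treats within-person correlation as a nuisance. It does not estimate how much the effect of a component varies between people, and it gives no effect for a named person. The descriptive individual results do not fill the gap:

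- each is a comparison with run-in, not of one component with another;
- the text does not say whether the CI is within a person or across people, or whether it allows for autocorrelation;
- no rule states when a component counts as the most effective for a participant;
- nothing separates true differences between people from night-to-night noise.

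Heterogeneity of response is a main reason given for the N-of-1 design, participants receive personal reports, and the results are meant to inform later N-of-1 work. Without an estimator, the trial could end with no heterogeneity result and with individual rankings of unknown reliability.

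**Working it through.** **Inputs from the documents.** Within-person SD at most 2 h, AR(1) correlation 0.95, 28 nights per component, 30 per arm, effect size 0.7, 80% power, alpha 0.05 (section 12); sequences ABCCBA and CBAABC in 2-week blocks (section 8); 2-week run-in (section 9).

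**Assumptions.** True between-component differences vary between people with SD τ = 0.5, 0.7 or 1.0 h. The documents give no value. Nights are complete. AR(1) of 0.3 and 0.5 are used as milder cases.

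**1. The plan's own figure.** The mean of the 28 × 28 AR(1) correlation matrix at 0.95 is 0.654. Reading 0.7 in SD units, two-sided, n per arm = 2 × 0.654 × (1.96 + 0.842)² / 0.7² = 20.95, so 21. Power at 30 per arm is Φ(0.7 / √(2 × 0.654 / 30) − 1.96) = 91.8%. Reading 0.7 as hours with SD 2 h gives 84 per arm. Neither reproduces 30 per arm at 80%. The contrast, units, sidedness and any multiplicity adjustment are not stated. The point here does not depend on that figure; it borrows only the SD and the correlation.

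**2. What the GEE shows.** In 100 simulated trials of 60 people with a mean effect of 0.7 h for every component (daily correlation 0.5, assumed), the GEE coefficients averaged 0.72, 0.71 and 0.70 h with no heterogeneity. With a between-person effect SD of 1 h (assumed) they averaged 0.67, 0.69 and 0.68 h, although each component was then truly best for about one third of people. The mean standard error rose from 0.14 to 0.18-0.19 h, but stronger autocorrelation can also raise a standard error, so that is not an estimate of heterogeneity.

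**3. Precision of one person's comparison.** For two component means, v = Var(mean 1) + Var(mean 2) − 2 Cov. At SD 2 h and AR(1) 0.95 in ABCCBA:

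- A vs B: 1.656 + 1.840 − 2 × 1.136 = 1.22, SE 1.11 h
- B vs C: 1.840 + 2.616 − 2 × 1.514 = 1.43, SE 1.20 h
- A vs C: 1.656 + 2.616 − 2 × 0.738 = 2.80, SE 1.67 h

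CBAABC gives the same values with A and C exchanged. Against run-in the SE is 1.7 to 2.3 h. A CI that treated nights as independent would use √(2 × 4 / 28) = 0.53 h for a between-component difference, two to three times too small.

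**4. Share of observed variation that is real.** Share = τ² / (τ² + v). For τ = 0.7 h at AR(1) 0.95: 0.49 / (0.49 + 1.22) = 29% and 0.49 / (0.49 + 2.80) = 15%.

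| Case | τ = 0.5 h | τ = 0.7 h | τ = 1.0 h |
|---|---|---|---|
| AR(1) 0.95, v = 1.22 to 2.80 | 8-17% | 15-29% | 26-45% |
| AR(1) 0.3, v = 0.49 to 0.51 | 33-34% | 49-50% | 66-67% |

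**5. Ranking by raw means.** If one component is truly 0.7 h better than the other two (assumed), the highest raw mean identifies it with probability 0.84 with independent nights, 0.67 at AR(1) 0.5 and 0.53 to 0.59 at 0.95. Chance is 0.33.

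**6. What shrinkage alone buys.** At τ = 0.7 h and AR(1) 0.95, the root mean square error of a raw individual difference is 1.11 to 1.67 h. Giving everyone the group mean has error 0.70 h (τ itself). Shrinking the raw difference gives √(τ²v / (τ² + v)) = √(0.49 × 1.22 / 1.71) = 0.59 h to √(0.49 × 2.80 / 3.29) = 0.65 h.

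**The case against.** The strongest reply is that the plan is not GEE-only. It reports individual changes with 95% CIs and gives each participant a report by component. A CI is the usual guard against reading noise as effect, and ranking raw means beats chance in every case in step 5. This stands. A reader might infer that the trial can say nothing about individuals; the documents do not support that.

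A reader might also infer that the GEE is the wrong model and should be replaced. It is not. The Primary Aim is an average, the sample size is based on GEE tests, and heterogeneity is not a listed aim.

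Nor does the plan say that it would present the spread of raw individual changes as heterogeneity. The gap is that no estimator is named, not that a biased one has been chosen.

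Finally, it is tempting to say that shrinkage halves the error of individual estimates. Against raw means it roughly does, but the group mean alone already has error 0.70 h, so the gain over ignoring individual data is 0.05 to 0.11 h. Those figures also treat the variances as known and shrink raw means; they do not measure how the mixed model proposed below would perform.

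None of this supplies a heterogeneity estimate, a between-component contrast or a rule for the best component.

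**Conclusion.** The concern holds as a mismatch between the stated goal and the analysis. Sections 3 and 4 promise to evaluate heterogeneity and identify each person's best component. Section 12 estimates no between-person variance of effect, and its individual results are descriptive, made against run-in, with an unspecified CI. The primary analysis is unaffected.

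The size depends on assumptions. The 2 h SD is a stated maximum, so the standard errors of 1.1 to 1.7 h are upper values at AR(1) 0.95. The real share runs from 8% to 45% over τ of 0.5 to 1.0 h at that correlation, and is about 50% at AR(1) 0.3 with τ = 0.7 h. In these cases a substantial part of what a participant would see as a difference between components is noise, and the plan has no step that would show how much. That no heterogeneity estimator is planned does not depend on any of these numbers.

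**What to change.** Keep the GEE as the primary analysis. Add to section 12 a supplementary linear mixed model for daily sleep duration that pools both sequences, with fixed component and time terms, a random participant intercept, random participant-by-component effects and AR(1) residuals. State that pooling departs from the arm-by-arm analysis for this model only.

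- Report the participant-by-component SD with its interval as the heterogeneity result.
- In the personal reports, show between-component individual estimates with intervals, and the probability that each component is best, alongside the observed data.
- State whether the planned 95% CIs are within or across people, and how they allow for autocorrelation.

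The cost is SAP wording and modest programming on data already being collected. The downsides are that individual estimates are pulled toward the group mean and that the variance component will be imprecise with 60 people, which is why its interval must be shown. If the model is not added, sections 3 and 4 should promise a descriptive individual summary only.
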